Grating Acuity Test - Visual acuity will be tested using a standard grating test. Subjects will be presented with a 10°x10° square window filled with either a horizontal or vertical grating, located 5° from the fixation point on a computer screen in their hemianopic or intact side. Gratings will start from 0.2 cycles per degree and progress to larger sizes of 0.5, 1.0, 1.5, 2.0, 2.5, 3.0, 4.0, then 5.0 cycles per degree. The test will comprise of 5 trials for each grating. Subjects will be asked to identify whether the grating is horizontal or vertical by either pushing buttons on a response pad or verbally. Responses will be recorded for each question.

Virtual Reality (Visual Field) Progress Test - At the end of each rehabilitation session, subjects will perform a brief 5-minute test using the VR system to

Color Vision Test - The color vision test will be administered on a computer. While focused on a central fixation point, subjects will be presented with a colored $10^\circ \times 10^\circ$ block located 5° in the anopic hemifield and be asked to verbally identify the color. A member of the research team will record these responses. The color in each trial will be randomly picked among the color choices of white, black, red, orange, yellow, green, blue, and violet. Each color will be displayed at least 3 times.

Shape Recognition Test - Subjects will be presented with basic shapes in their hemianopic side on a computer monitor. Shapes will be colored black and be displayed on a white background in a $10^\circ \times 10^\circ$ square window located 5° in the previously hemianopic side. Subjects will be asked to fixate on a central point and verbally identify each object or express uncertainty. Verbal responses will be recorded for later analysis. During this test, subject responses may be audiotaped in order to capture their responses. This test will consist of 20 trials.

Questionnaires

The NEI VFQ-25 and VA LV VFQ-48 questionnaires are designed to assess the taker's quality of life regarding limitations due to low vision.

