The virtual reality headset and headphones will provide visual and auditory stimulation used in the rehabilitation training. Each rehabilitation session will consist of 200 trials. At the end of each rehabilitation session, subjects will perform a brief 2-minute VR visual field progress test with the VR system to track rehabilitation progress. The rehabilitation will be considered complete once patients can reliably detect stimuli 45° in the hemianopic field.

If patients cannot detect stimuli at 15° by the end of 30 days of rehabilitation, they will repeat the rehabilitation for one more month, in order to determine if the slow progress or lack of progress is caused by simply not spending enough time performing rehabilitation.

Study Session 63: Post Rehabilitation Tests - Subject visual field did not increase (1 hour)

If no visual field improvement (measured by virtual reality visual field progress tests) has occurred at the end of the 2nd round of rehabilitation, subjects will complete one last visit, where they will be given the

NEI VFQ-25 and VA LV VFQ-48 questionnaires to complete. This visit will occur on the Wake Forest Baptist Medical Center campus.

Study Session 33: Post Rehabilitation Tests - Subject visual field increase (1.5 hours)

If a subject shows visual field expansion in the virtual reality visual field progress test, subjects will be given a **Peripheral Visual Field Test, NEI VFQ-25 and VA LV VFQ-48 Questionnaires** in order to measure visual field expansion and improvements in quality of life.

In previous animal studies, rehabilitated hemianopic animals could only detect spatial frequencies of 2 cycles/degree compared to over 5 cycles/degree in the (normal) intact animals. We hypothesize the subcortical visual pathway mediating the restored visual functions may not have the same capabilities as the visual cortex it is replacing. Therefore, recovered vision may have lower visual acuity. The different pathways involved in cross-modal rehabilitation may also affect abilities for shape recognition in the newly recovered visual field. We will explore whether this is the case with a simple **shape recognition test, visual acuity test, and color vision test** during this visit. Subjects will complete this visit on the Wake Forest Baptist Medical Center campus.

Study Session 34: Humphrey Visual Field Post-Intervention Test (1 hour)

Subjects will report to an optometrist for a **Humphrey Visual Field** perimetry test.

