Study Session 35: 3 Month Post-Intervention Follow-up Tests (1 hour)

Subjects will complete a follow-up visit 3 months after the end of rehabilitation on the Wake Forest Baptist Medical Center campus. The follow-up visit will consist of a peripheral visual field test, and NEI VFQ-25 and VA LV VFQ-48 questionnaires.

Study Session 36: 6 Month Post-Intervention Follow-up Tests (1 hour)

Subjects will complete a final follow-up visit 6 months after the end of rehabilitation on the Wake Forest Baptist Medical Center campus. The follow-up visit will consist of a peripheral visual field test, and NEI VFQ-25 and VA LV VFQ-48 questionnaires.

Outcome Measure(s)

The primary outcomes for all participants will be the visual field measurements from Humphrey Visual Field and peripheral frame test, with comparisons made before (visits 1 and 2) and after treatment (visits 34 and 35 or visits 63 and 64).

Secondary outcome measures will include differences in quality of life questionnaire results from before (visit 1) and after treatment (visit 33 or 63) and changes in VR progress test results during the course of rehabilitation (visits 3-32 and 33-62 if a subject repeats rehabilitation).

Exploratory outcome measures will be collected in subjects with restored visual fields. The qualities of recovered visual field will be examined with visual acuity, color recognition, and shape recognition tests after rehabilitation (visit 33 or 63).

Analytical Plan

Results will be analyzed initially using descriptive statistics. The improvement of visual detections will be assessed by using a two-way ANOVA on the percentages of visual detections to stimuli presented in the hemianopic hemifield in the peripheral visual field tests before and after rehabilitation. Comparisons for subjects will be done using chi square tests for proportions, and t-tests or ANOVA procedures for continuous variables. Other inferential statistical analysis will be conducted as appropriate.

Human Subjects Protection

Subject Recruitment Methods

Protocol version: 2

Protocol updated 7.01.20

Subjects with homonymous hemianopia on either the left and right side of the visual field will be recruited using resources from Wake Forest University Health Sciences' Clinical and Translational Science Institute (CTSI). Members of the PI's research team will perform recruitment. Coordination of potential participants' visit will be done by phone or in person conversation or by email.

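### The grating acuity test (two choices, 5 trials per grating, top grating 5.0 cycles/degree) has no scoring rule, so the size and direction of its error are undefined, and the intact side may be censored

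*Combined protocol and SAP*

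**What the plan says.** The Grating Acuity Test paragraph (Combined protocol and SAP, Tests) describes a two-alternative task: "Subjects will be asked to identify whether the grating is horizontal or vertical". The window is "located 5° from the fixation point on a computer screen in their hemianopic or intact side". The series starts at 0.2 cycles/degree and is to "progress to larger sizes of 0.5, 1.0, 1.5, 2.0, 2.5, 3.0, 4.0, then 5.0 cycles per degree", which makes nine gratings. On trial numbers it says only "The test will comprise of 5 trials for each grating", and on scoring only "Responses will be recorded for each question".

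Study Session 33 gives the reason for the test. Rehabilitated animals "could only detect spatial frequencies of 2 cycles/degree compared to over 5 cycles/degree in the (normal) intact animals", and the protocol infers: "Therefore, recovered vision may have lower visual acuity".

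Outcome Measure(s) places acuity in the lowest tier: "Exploratory outcome measures will be collected in subjects with restored visual fields". The test is scheduled only after rehabilitation, and the Analytical Plan does not mention it.

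**The concern.** With two possible answers, a subject who sees nothing is right half the time. Five trials per grating are few for telling that subject from one who sees the grating, and the plan does not say how the five answers become an acuity value. A lenient rule credits guesses; a strict rule rejects gratings that were seen.

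Other tests in the same section are more explicit. The Peripheral Visual Field Test states its 5 trials per location for both sides and adds 5 trials with no stimulus. The Shape Recognition Test lets the subject say that he or she is unsure. The grating test has neither feature. There is also no pre-treatment acuity score to show what chance performance looks like.

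The series stops at 5.0 cycles/degree, while the intact comparator that motivates the hypothesis lies above that value. If human intact-side acuity is also higher, every such subject scores 5.0.

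At stake is the estimate of how much poorer recovered vision is than intact vision. About 5 completers are hoped for and the results are meant to inform later studies, so one or two wrong values would matter.

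**Working it through.** **The plan's own figure.** No error rate or precision is stated for this test. The only sizing figure, in Sample Size, is a 95% interval half-width of 0.35 for a success proportion. It reproduces as 1.96 × √(0.8 × 0.2 / 5) = 0.351, but has no bearing on acuity.

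**Inputs from the documents.** Two choices, so the guess rate is 0.5; 5 trials per grating; nine gratings (0.2, 0.5, 1.0, 1.5, 2.0, 2.5, 3.0, 4.0, 5.0); animal values of 2 (recovered) and above 5 (intact) cycles/degree.

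**Assumptions, because the plan is silent.** The pass mark is 5/5 or at least 4/5. The score is either the highest grating passed or the last one before the first failure. The illustrative subject has a true limit of 2.0, passes every grating up to 2.0, and guesses at the four above it (2.5, 3.0, 4.0, 5.0).

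**Passing one grating by guessing.**
- 5/5: 0.5⁵ = 1/32 = 3.1%
- At least 4/5: (5 + 1)/32 = 18.8%

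**Overstating a true limit of 2.0.** Under stop at first failure, only the 2.5 grating has to be guessed. Under highest passed, any one of four suffices, with probability 1 − (1 − p)⁴.

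| Pass mark | Stop at first failure | Highest passed |
|---|---|---|
| 5/5 | 3.1% | 1 − 0.96875⁴ = 11.9% |
| At least 4/5 | 18.8% | 1 − 0.8125⁴ = 56.4% |

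**The opposite error.** A subject who is 90% correct on a visible grating fails a 5/5 mark with probability 1 − 0.9⁵ = 41%. Even at 95% correct, passing all five gratings up to 2.0 means 25 correct answers in a row: 0.95²⁵ = 28%. So 5/5 with a stop understates acuity 72% of the time.

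**Trials shared between sides.** If the 5 are split, each side has 2 or 3. A perfect score by guessing then has probability 0.5² = 25% or 0.5³ = 12.5%.

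**Ceiling.** The highest recordable score is 5.0, so against a recovered value of 2 the largest measurable gap is 5 − 2 = 3 cycles/degree. If the intact side truly resolves 6, 8 or 10 (assumed; the documents give no human value), the gap is understated by 1, 3 or 5.

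**Pooling across gratings.** With 5 trials per side, the illustrative subject gives 4 × 5 = 20 guesses above the limit. The chance of at least 15 right is about 2%, and of at least 18 right 211/2²⁰ = 0.02%. The full set of answers is far more informative than any one grating.

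**The case against.** The strongest reply is that the test itself may be adequate and only the scoring rule is missing. Answers are recorded trial by trial, so a chance-corrected threshold can be computed without altering the test, and the pooling calculation shows that the series carries real information. This largely stands, and the fix relies on it. It does not settle two points: the number of trials on each side is not stated, and no scoring can recover acuity above a 5.0 ceiling.

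Three stronger readings are tempting and are not supported:

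- A reader might take 56% as the error of the test. It belongs to one lenient pair of rules that the plan does not adopt; the other three combinations shown give 3.1% to 18.8%.
- A reader might infer that guessing must inflate the recovered side, so that guessing and ceiling together always shrink the gap. That direction depends on the rule. A strict 5/5 mark lowers scores, and on the recovered side this would widen the gap.
- A reader might infer that the intact side will hit the ceiling, or that a ceiling defeats the hypothesis. The comparator is an animal value, so censoring is possible but not shown. A recovered score of 2 against an intact score of 5 or more would still show lower acuity.

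It is also fair to say that no primary or secondary outcome, and no sample-size figure, depends on this test.

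**Conclusion.** The point holds as a low-priority one. As written, a single grating cannot reliably separate seeing from guessing, and without a scoring rule the error is undefined in both size and direction. For a true limit of 2.0 cycles/degree, overstatement by guessing runs from 3.1% to 56% over the four rules considered, while the strict mark misses a visible grating 41% of the time at 90% accuracy. These figures assume pure guessing above the limit, independent trials and 5 trials on the side in question; shared trials would make matters worse. Censoring at 5.0 is a possibility raised by the plan's own animal value, and would affect the magnitude of the gap, not its sign.

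**What to change.** - State at least 5 trials per grating on each side.
- Estimate one threshold per side from all of that side's trials, using a psychometric curve with its lower asymptote fixed at 50%, and put this in the Analytical Plan.
- On the intact side, add gratings finer than 5.0 cycles/degree. Report any score still at the top of the series as at or above the top grating.
- Optionally, use 10 trials per grating per side.

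**Cost.** Analysis time and a change to the test script. Nine gratings at 5 trials on two sides is 90 trials. If 5 per side is already intended, nothing is added beyond the finer gratings. If the 5 are now shared (45 in total), 45 are added, about 4 minutes at an assumed 5 seconds per trial, plus the finer gratings. The 10-trial option needs 180 trials, so 90 to 135 more, or about 8 to 11 minutes, again before the finer gratings. The visit is planned at 1.5 hours and already holds several other tests, which favors the 5-per-side version with the fitted curve.

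### The exploratory shape and colour tests have no intact-side reference, so they cannot show whether naming in the recovered field is poorer than the subject's own cortical vision

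*Combined protocol and SAP*

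**What the plan says.** Under Tests, the Shape Recognition Test states "Subjects will be presented with basic shapes in their hemianopic side on a computer monitor", in a "square window located 5° in the previously hemianopic side". On length: "This test will consist of 20 trials". The Color Vision Test uses a block "located 5° in the anopic hemifield and be asked to verbally identify the color", with eight colours, and "Each color will be displayed at least 3 times". Both are scored from spoken answers.

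The Grating Acuity Test differs. Its window is "located 5° from the fixation point on a computer screen in their hemianopic or intact side". The peripheral field test and the VR progress test also use both sides.

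The Study Session 33 section gives the purpose. It hypothesises that the subcortical pathway "may not have the same capabilities as the visual cortex it is replacing", infers that acuity may be lower, adds that shape recognition may also be affected, and says the shape, acuity and colour tests will explore this. Outcome Measure(s) makes all three exploratory, done after rehabilitation only, in subjects with restored fields. Neither baseline testing nor the 3- and 6-month visits include a shape or colour test, and the Analytical Plan names no comparison between sides.

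**The concern.** Asking whether one pathway matches another calls for a reference. The animal evidence in the same section is itself a comparison: 2 cycles/degree in rehabilitated animals against over 5 in intact ones. For shape and colour in humans the plan collects only one half of that comparison.

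A low blind-side score could reflect the recovered pathway. It could also reflect viewing away from fixation, naming or attention difficulty after brain injury, a colour-vision deficiency that was there before, or the display. An intact-side run in the same person shares most of these factors; a blind-side score alone cannot separate them. Because the tests are given at one visit only, an intact-side score not taken then cannot be recovered by later analysis.

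**Working it through.** **The plan's own figure.** The only sizing figure is in Sample Size: n = 5, success rate 0.80, 95% half-width 0.35. It reproduces: 1.96 × √(0.8 × 0.2 / 5) = 0.3506. It concerns the success proportion, and this point does not depend on it.

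**Reference available for each test (Tests section)**

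| Test | Side shown | Trials | Own intact-side reference |
|---|---|---|---|
| Grating | hemianopic or intact | 5 per grating | yes |
| Colour | hemianopic only | 8 × at least 3 = at least 24 | no |
| Shape | hemianopic only | 20 | no |

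**What a blind-side score can say.** The protocol gives no expected scores, so the following are assumptions. Take 14/20 shapes correct on the blind side: 70%, exact 95% interval 46 to 88%. The deficit is the intact-side score minus 70%.

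| Assumed intact-side score | Deficit (percentage points) |
|---|---|
| 100% | 30 |
| 90% | 20 |
| 80% | 10 |
| 70% | 0 |

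The planned data are identical in all four rows. The deficit can be read only against an assumed ceiling.

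**What the added trials would give.** Half-width of the difference within one subject, unpaired normal approximation: 1.96 × √(p_b(1 − p_b)/n + p_i(1 − p_i)/n), where p_b and p_i are the blind-side and intact-side proportions correct. Assume p_b = 0.70.

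- Shape, n = 20 per side: p_i = 0.95 gives 25 ± 22 points; p_i = 0.90 gives 20 ± 24 points.
- Colour, n = 24 per side: p_i = 0.95 gives 25 ± 20 points; p_i = 0.90 gives 20 ± 22 points.

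**Across subjects.** The smallest two-sided sign-test p is 2 × 0.5^n: 0.0625 with 5 subjects and 0.031 with 6. Only subjects with restored fields take these tests. At the assumed 80% success, 5 completers yield 0.8 × 5 = 4, for whom the smallest p is 2 × 0.5^4 = 0.125.

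**Added load.** 24 + 20 = 44 trials at minimum. At an assumed 5 s each, 44 × 5 = 220 s, about 3.7 minutes; at 10 s, 440 s, about 7.3 minutes.

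**The case against.** The strongest reply is that the explicit inference in Study Session 33 is about acuity, and acuity has the intact side. For shape, the text says only that ability in the recovered field may be affected; colour comes in only through the list of tests. Outcome Measure(s) then asks for no more than an examination of the qualities of the recovered field. Blind-side trials serve that purpose: with eight listed colours, guessing among them gives 1/8 = 12.5%, so clear naming ability would be visible. Basic black shapes in a 10° window may also be near ceiling on the intact side, in which case the blind-side score approximates the deficit. The exclusion of people who cannot do the tasks or follow instructions reduces the naming and attention explanations.

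Most of this stands as a limit on scope. A reader might infer that the plan cannot answer its question about recovered vision at all, or that the two tests are uninformative. The documents support neither reading. Two things remain. The near-ceiling argument is an assumption that the protocol neither states nor checks, and it is less safe for eight-way colour naming when no colour-vision screen is listed. And the exclusion criteria do not remove the effect of viewing away from fixation or of the display.

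The remedy also has limits. Mirrored trials do not show whether ability at 5° was recovered or residual, since neither test is done before rehabilitation. The Humphrey test covers the central 30° before and after, but it measures light detection, not naming.

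**Conclusion.** The point holds for shape, which the hypothesis names, and for colour as a listed companion test. Each can show whether naming exists in the recovered field; neither can show whether it is poorer than the subject's own cortical vision.

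The size of any missed or misread deficit is unknown. The 0-to-30-point range rests on an assumed blind-side score of 14/20 and assumed intact-side scores of 70 to 100%. A reader might also infer that intact-side trials would permit a formal test; with about 5 subjects they would not, and single-subject differences would carry half-widths of roughly 20 to 24 points under the assumptions above.

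This is a cheap improvement to exploratory measures. It bears on what the study can pass on to later designs, which Sample Size gives as its purpose.

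**What to change.** At the same post-rehabilitation visit, present the same colour and shape stimuli at the mirrored 5° position in the intact field, with the same number of trials per side and the side chosen at random. In the Analytical Plan, state that each subject's blind-minus-intact difference will be reported descriptively for both tests, and for gratings too. In the Grating Acuity Test, "The test will comprise of 5 trials for each grating" should say whether this is per side: nine gratings give 9 × 5 = 45 trials in total, or 90 if per side.

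The cost is the 44 or more additional trials in a 1.5-hour visit that already holds the peripheral field test, two questionnaires and three visual tests, with slightly more fatigue. The same computer set-up serves, and no extra visit is needed. The report should say that the comparison does not separate recovered from residual vision at 5°.

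### Minor: the shape test lets subjects decline to name a shape, so when recovered vision is faint the number correct can depend heavily on the subject's caution; recording a best guess plus a confidence answer would fix this cheaply

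*Combined protocol and SAP*

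**What the plan says.** Under Tests, Shape Recognition Test, the plan states: "Subjects will be presented with basic shapes in their hemianopic side on a computer monitor". The response rule is "Subjects will be asked to fixate on a central point and verbally identify each object or express uncertainty", and the length is given as "This test will consist of 20 trials". On handling of the answers it says only: "Verbal responses will be recorded for later analysis". The number and identity of the shapes, the scoring of an uncertain answer and the level expected by guessing are not given there or in the Analytical Plan.

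The Grating Acuity Test is worded differently: "Subjects will be asked to identify whether the grating is horizontal or vertical by either pushing buttons on a response pad or verbally". It mentions no uncertain option, but does not say what happens if a subject gives no answer.

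The purpose is set out under Study Session 33: "The different pathways involved in cross-modal rehabilitation may also affect abilities for shape recognition in the newly recovered visual field". Outcome Measure(s) gives the status of these tests: "Exploratory outcome measures will be collected in subjects with restored visual fields". They are scheduled after rehabilitation only.

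**The concern.** When a subject may decline, the number correct reflects two things: how much the subject sees, and how sure the subject must feel before speaking. The two matter equally little when vision is clear, because few trials are declined. They part company when vision is weak and graded. Study Session 33 expects the pathway behind the restored field to be possibly less capable than visual cortex and asks whether shape recognition suffers. A low score could then mean little shape vision, or a cautious speaker with useful shape vision.

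Nothing else in the design separates these readings. Shapes are shown only on the hemianopic side, whereas gratings are shown on either side, and there is no shape test before rehabilitation. The Sample Size section hopes for at least 5 completers, too few for differences in caution to average out. The same section says the findings will inform the design of later studies.

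**Working it through.** The plan gives no figure for this test beyond its 20 trials, so there is none to reproduce. The following is an illustration under stated assumptions.

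**Input from the protocol.** 20 trials, with an uncertain answer allowed.

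**Assumptions.** K equally likely shapes (K = 4, then 3 and 8). Each trial gives K independent normal signals with unit variance, the true shape's mean being raised by d'. The subject picks the most probable shape and speaks only if its probability is at least c.

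**Formulas.**
- True accuracy p = ∫ φ(x − d') Φ(x)^(K−1) dx. For K = 4 and p = 0.70, d' = 1.49.
- The probability of shape j given the signals is exp(d'·x_j) / Σ exp(d'·x_k).
- Score with uncertain counted as wrong = P(largest probability ≥ c and choice correct), obtained by simulation.

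**Scores for K = 4, uncertain counted as wrong.**

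| Answers only if at least this sure | True accuracy 70% | True accuracy 90% |
|---|---|---|
| 50% | 62% | 89% |
| 60% | 54% | 86% |
| 70% | 44% | 83% |
| 80% | 32% | 78% |
| 90% | 18% | 69% |

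Out of 20 trials, a true accuracy of 70% means 20 × 0.70 = 14 correct on average if every shape is named. It becomes 20 × 0.44 = 8.8 at the 70% criterion and 20 × 0.18 = 3.6 at the 90% criterion.

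**Dropping the uncertain trials moves the score the other way.** At true accuracy 70% and criteria of 70, 80 and 90%, the share of trials answered is 51, 36 and 19%. Accuracy on the answered trials is 86, 90 and 95%. Neither scoring returns 70%.

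**What the declined trials contain.** At the 70% criterion, 100 − 51 = 49% of trials are declined, and the subject would have been right on 70 − 44 = 26% of all trials among them. That is 26/49 = 53% correct, against 25% by guessing. At the 90% criterion it is (70 − 18)/(100 − 19) = 52/81 = 64%. So under this model the declined trials hold real information, which is not collected.

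**Other numbers of shapes, 80% criterion, uncertain counted as wrong.**

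| True accuracy | K = 3 | K = 4 | K = 8 |
|---|---|---|---|
| 50% | 0.4% | 2% | 7% |
| 70% | 29% | 32% | 36% |
| 90% | 77–78% | 77–78% | 77–78% |

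The pattern is similar for 3 to 8 shapes: strong loss when vision is weak, modest loss when it is good.

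**The case against.** The strongest reply is that the opt-out is a legitimate choice. Naming a shape or admitting uncertainty measures reported recognition and keeps out lucky hits. A required answer measures discrimination, including guesses without awareness, and brings in a guessing floor (25% with four shapes). The plan does not say it wants the second. Responses are recorded, so correct, wrong and uncertain counts can all be reported, and a reader shown all three would be less easily misled.

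Much of this stands. The opt-out is not a flaw in itself, and reporting three counts would help. It would not supply accuracy on the declined trials, which must be asked for at the time. Collecting both a best guess and a confidence answer serves both purposes, so there is no need to choose between them.

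Three stronger readings are tempting, and the documents do not support them.

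- **That the score measures guessing as much as vision.** Suppose each shape is either fully identified (share s) or purely guessed. Guessing then adds 20(1 − s)/K correct answers. It matches vision only when s ≤ 1/(K + 1), which is 0.25 for K = 3 and 0.11 for K = 8. At s = 0.5 it adds at most 20 × 0.5/3 = 3.3 of 20.
- **That the grating test forces a choice, so the two results conflict.** The text offers two alternatives but is silent on non-answers, and no comparison of shape with grating scores is planned.
- **That cautious subjects would fail a pass mark.** The plan has none for shapes. A cut such as 9 of 20, derived from 25% guessing, would not suit data with declines, where a subject without shape vision could score near zero.

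**Conclusion.** The point holds as a minor, cheap improvement. The response rule lets caution enter the shape score, and the lost answers cannot be recovered afterwards. In the illustration, a true accuracy of 70% can be scored anywhere from 62% to 18% depending on the subject's criterion, while a true accuracy of 90% is scored from 89% to 69%.

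These sizes rest on assumptions that the protocol neither gives nor rules out: the number of shapes, the Gaussian model, the range of criteria, and scoring uncertain as wrong. A subject who speaks freely would lose little. Shape recognition is exploratory and assessed only in subjects with restored fields. No primary or secondary outcome depends on it.

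**What to change.** Keep the 20 trials and keep the uncertainty report. Then:

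1. Fix the list of shapes, state it in the protocol, and tell it to subjects before the test (for example four shapes, five times each, in shuffled order).
2. On every trial record one named shape, as a best guess if the subject is uncertain, and then sure or unsure.
3. Report percent correct over all 20 trials against 1/(number of shapes).
4. Report separately the share named correctly and sure. This approximates the score the present rule would give with uncertain counted as wrong; asking for a guess first may shift confidence slightly, so the match is not exact.

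The cost is a changed instruction and one extra prompt per trial. The all-trials score also gains a guessing floor, but a known one.
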